## **3. Study design**

To address these objectives, we will conduct an observational cohort study in 1200 pregnant women who will be recruited at the first antenatal care (ANC) visit from the Gugulethu and one additional facility in the Hanover Park subdistrict of the Metro Region (to be identified in conjunction with provincial and local health authorities) Midwife Obstetric Units in Cape Town (n=600 pregnant women per site). We will follow the enrolled women through 12-months post-delivery.

**Setting.** The study will take place in two urban townships in Cape Town (Gugulethu and Hanover Park) with high HIV incidence that span the different socioeconomic, cultural, and ethnic groups in South Africa.

- Site 1: Gugulethu Midwife Obstetrics Unit (MOU)**
- Site 2: Hanover Park**

We selected those communities because of the high HIV prevalence there in pregnant and breastfeeding women, and because of the high number of mothers visiting every month for ANC and labour/delivery. Further, our team has several years' experience implementing research studies in those MOUs which will facilitate the integration of the study there. In 2017, Gugulethu saw over 3300 new ANC consultations per month, and 72%

(n=2300) are HIV-negative. Hanover Park has saw over 4900 new ANC consultations/month of which 87% are HIV-negative (n=4200). Considering our experience and patient flow, we are confident that at least 60 women/month per facility can be enrolled. Further, Drs. [name], [name] and colleagues have conducted research in the Gugulethu and Hanover Park communities for more than a decade and have substantial experience partnering with local health services. Building on this platform, we will use existing infrastructure in each clinic, including capacitating existing clinical providers, pharmacists and counselors, to provide PrEP care to pregnant and breastfeeding mothers. We will hire study staff to assist in the coordination, data management, and overall quality assurance of the counseling, drug provision and participation follow-up.

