**Step 9: For all participants who decide to take PrEP, the study nurse will draw blood to test for baseline creatinine tests**

- Women with low creatinine can participate in the study but can only receive PrEP if their eGFR >60mL/min
- Test results will be received in 24-48 hours. If eGFR <60mL/min then the nurses will call participant to return and immediately stop using PrEP until they have a normal creatinine result (can return in following month)

**Step 10:** Participants who opt to take PrEP will receive counselling on the risks and benefits of PrEP. Following the counseling they will be asked: “Do you want to start taking PrEP today to prevent HIV? You will need to take it daily for it to be effective.” Her response will be recorded.

If yes:

1. The nurse will provide the participant with a 1-month supply of TDF-FTC and invite her to return in 1 month for her next study visit (after then they will receive 3 months prescriptions to correspond with their quarterly PrEP-PP study visit).
2. Nurses will provide contact information to the participant and ask her to call to report any side effects or adverse events while on PrEP, and nurse will track and report serious adverse events to study PIs, Pediatrician, and Obstetrician to decide on how to treat women and infants who have adverse events.

If she says she does not want to start PrEP, woman will be in the deferred PrEP arm:

1. The nurse will schedule her to return in 3 months for the follow-up study visit

**Step 10:** Participants will receive study staff contact information, instructions to call with any questions, and will be scheduled for their next visit in 1 month if on PrEP, or 3 months if not on PrEP, for the next study visit

**Step 11:** The study counselor will provide the mother with an appointment card and invitation for her partner to return to receive couples' HIV testing and counseling (if in a relationship). The session will end by encouraging the client to implement her/his risk-reduction plan (including PrEP if applicable and consistent condom use, couples testing) to prevent HIV acquisition.

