**Step 12:** The participant will receive a snack and reimbursement for her time and transportation (up to R250 in a Shoprite voucher, refreshment and reimbursement for transportation) which is in line with our ongoing research at these sites. Further, we will combine the study visits with existing ANC or post-partum/well-baby visits to minimize the travel to the facilities outside of normal clinical checkups.

2. For follow up return visits:

Follow up visits will be at 1 month after baseline (to coincide with ANC visits) then after two months after birth then every 3 months thereafter (to coincide with post-partum, well-baby visits).

COVID update: During the COVID-19 lockdown, we will offer women the option of participating in interviews over the phone with participants who are willing and unable to attend the study visit. The interviewer will be in a private room and will ask the participant to be in a private, quiet space. The interviewer is an experienced isiXhosa -speaking research assistant and interviews will be conducted over the phone while the interviewer collects the data on the tablet using RedCap. Updated processes include:

- **Calling participants who miss study visits to assess if they wish to participate a phone interview (and schedule a time when they can be alone in a quiet place for 20-30 minutes)**

The interviewer will ascertain the participant ID and date of birth to ensure that they are speaking with the participant.

**Step 1:** In ANC: Healthcare providers provide counseling on HIV prevention and treatment at each ANC visit including HIV testing, as part of standard of care. In post-natal care and well-baby visits women may not receive regular HIV testing and messages and will receive this within step 2 (with study counselor). Following their ANC visit, enrolled women will be invited to attend the study site in each MOU to do the follow-up visit including the survey and prescription and adherence counseling (if on PrEP).

**Step 2:** Survey at each visit in a private study room

**Step 3:** In the study room, the study counselors will provide PrEP-specific counseling including adherence counseling for those on PrEP (and management of side effects), or counseling about the risks and benefits of PrEP for women not yet on PrEP. Women not on PrEP will be asked if they are interested in starting PrEP at this visit.

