**Table 1. Study measures for PrEP-PP for AIM 1**

Primary Outcomes	Measurement	Source	Frequency
PrEP initiation	# of women who initiate PrEP over time / total # of women in active cohort = proportion of women who initiate PrEP	Electronic provider log (REDCap)	Quarterly
PrEP continuation	# of women on PrEP who return for study visits (do not miss more than 1 visit) / total # of women in active cohort who are prescribed PrEP= proportion of women on PrEP who continue in PrEP study	Electronic provider log (REDCap)	Quarterly
PrEP persistence (subjective)	# of women reporting taking PrEP in $\geq 5$ out of last 7 days or $\geq 25$ out of last 30 days (self-reported)/ total woman-time on PrEP in active cohort = PrEP persistence rate (subjective)	Electronic provider log (REDCap)	Quarterly
PrEP persistence (objective)	# of women taking PrEP who have $\geq 600$ fmol/punch (~7 doses/week) from DBS TDF-DP at 3rd trimester, delivery, and 6 weeks postpartum (and during sexual risk periods during that time) / total woman-time on PrEP in active cohort = PrEP persistence rate (objective)	Lab analysis of TDF-DP measures	Yearly and end of study
Secondary Outcomes			
Prevention effective persistence	4. # of women reporting adherence to PrEP (as per PrEP persistence subjective measure)/ total woman-time reporting sexual activity in past 30 days	Electronic provider log (REDCap)	Quarterly
	5. # of women having TDF-DP in DBS (as per PrEP persistence objective measure)/ total woman-time reporting sexual activity in past 30 days	Lab analysis of TDF-DP measures	Yearly and end of study

Prevention effective continuation	# of women who don't miss any PrEP study visits/ total woman time reporting sexual activity in prior visit	Electronic provider log (REDCap)	Quarterly
Predictors of attrition at key steps in the PrEP cascade	Individual, pill/study and disease specific predictors of PrEP initiation, continuation and persistence	Study CRFs and in-depth interviews (month 7 and12) (mixed methods)	End of study
Healthcare provider attitudes and knowledge about PrEP in pregnancy	Provider knowledge about PrEP and barriers/facilitators to PrEP prescription in ante and postnatal care	In-depth interviews	Year 1 of study
HIV outcomes	HIV testing data: HIV-uninfected, HIV incidence in mother and child (if mother seroconverts) compared by PrEP use/non-use	Electronic provider log (REDCap)	End of study

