Health outcomes and adverse events	Any side-effects, change in creatinine clearance, any negative maternal or neonatal outcomes (for mother and infant) compared by PrEP use/non-use	Electronic provider log (REDCap)	Weekly and quarterly
Infant growth outcomes	Measure infant weight, length, z-score and any adverse events in infants compared by PrEP use/non-use	Electronic provider log (REDCap)	Weekly and quarterly

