#### ***Methods/Approach:***

- (1) Study flow figure (see Continuation Flowcharts)
- (2) Number screened per week and month (target= 18 per week, 72 per month) vs number enrolled
  - a. The projected sample size for the study is 1200 women enrolled until 12-months postpartum (estimated mean of 18-months follow-up).
- (3) Subjects initiating PrEP compared to those who do not
  - a. Estimated that 60% of women (n=720) will initiate PrEP during the study period (versus approximately 40% who will not).
- (4) Continuation and persistence by group
  - a. Assumed that approximately 75% of women on PrEP (n=540) will continue on PrEP at 12-months (defined as not missing >1 study visit among women on PrEP);
  - b. Assumed that 70% of those retained in care (n=378) will adhere to PrEP during at-risk periods.
- (5) Final completion rates
  - a. Compare final number of participants who enroll in study, who initiate PrEP, who are retained in care, and who adhere to PrEP to sample sizes needed to yield 80% power (i.e., n=1200, 720, 540, 378, respectively).
- (6) Number of subjects in analysis data sets
  - a. Consider number of participants that will potentially be excluded from analyses because of withdrawal from study, missing data on key covariates or outcomes, etc.

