- iii. **Disease-specific factors:** Collected from CRFs (in all participants, not just those who decide to take PrEP) on partner's HIV status (including knowledge of serostatus and uptake of couples testing and counseling), perceived risk of HIV exposure and acquisition, perceptions of PrEP efficacy, and stigma associated with PrEP and HIV. Collected from the sub-set of women participating in the IDIs.
- b. **HIV outcomes:** Describe the frequency of HIV outcomes, including maternal and infant incident HIV. Analyses will include pure-count and person-time approaches. While we expect the frequency of adverse HIV-related outcomes to be low, we will describe characteristics of women who did/did not acquire HIV, and consider further analyses using the approaches outlined.

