***Methods/Approach:***

Tabulation of adverse effects with each treatment group:

- (1) Number of events by type of event
  - Describe the frequency of any laboratory or self-reported side effects (e.g. changes in creatinine clearance, or self-reported side-effects [GI symptoms, headache, and etc]). Analyses will include pure-count and person-time approaches. Confidence intervals will be calculated following the method of Breslow and Day. We will also describe pregnancy (miscarriage, stillbirth) and infant outcomes over time (including birthweight, gestational age at delivery, pregnancy loss) by PrEP status (on/off PrEP and by persistence to PrEP)
- (2) Number of subjects by highest grade of event
- (3) Reasons for termination of treatment

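### HIV, maternal, birth and infant-growth outcomes are compared between women who chose PrEP and women who did not, with no committed adjustment, so the contrasts are confounded by self-selection

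*Combined protocol and SAP*

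**What the plan says.** Protocol section 3 states the design: "we will conduct an observational cohort study in 1200 pregnant women". Exposure is not assigned. At the baseline visit (protocol section 5, Step 10) the woman is asked whether she wants to start: "If she says she does not want to start PrEP, woman will be in the deferred PrEP arm". At follow-up visits (Step 3) the offer is repeated: "Women not on PrEP will be asked if they are interested in starting PrEP at this visit". SAP section 2.2 gives the expected split: "Estimated that 60% of women (n=720) will initiate PrEP during the study period".

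SAP Table 1 defines the HIV outcome as "HIV incidence in mother and child (if mother seroconverts) compared by PrEP use/non-use". Its rows for health outcomes and adverse events and for infant growth also end with "compared by PrEP use/non-use".

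The methods attached to these rows are brief. For HIV (SAP 2.5) and adverse effects (SAP 2.6): "Analyses will include pure-count and person-time approaches". Section 2.6 adds: "Confidence intervals will be calculated following the method of Breslow and Day". It also describes pregnancy and infant outcomes by whether the woman is on or off PrEP and by persistence. Infant growth has its row in Table 1 but no method or shell of its own. The adverse-event, HIV-test and birth-outcome shells in SAP section 4 hold numbers, percentages and a comment column for users and non-users. The adverse-event shell counts any PrEP in the preceding 30 days as use. The only adjusted column in the shells belongs to the table on PrEP uptake.

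**The concern.** The SAP itself expects the choice of PrEP to depend on risk. Aim 1 studies age, substance use, relationship status and the partner's serostatus as predictors of initiation, and the uptake shell adds STI diagnosis, number of partners and partner violence. Several of these bear directly on HIV acquisition, and some plausibly bear on birth outcomes. An unadjusted user/non-user contrast would therefore carry those differences with it, in either direction. PrEP could look less effective or more harmful than it is if higher-risk women choose it, or safer than it is if healthier women do.

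The wording makes a causal reading likely. The purpose of SAP 2.6 refers to adverse intervention effects, that of 2.7 to treatment effects, and nothing cautions that the groups are self-selected. Maternal and infant safety by PrEP status is a sensitive output, and the report templates in SAP section 4 allow it to go to the DSMB in that form.

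**Working it through.** **1. Groups.** The plan's figure reproduces: 1200 × 0.60 = 720 initiators, leaving 480. With a mean of 18 months each, that is 720 × 1.5 = 1080 and 480 × 1.5 = 720 person-years, 1800 in total.

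**2. Does any committed adjustment reach these contrasts?**
- *Covariates selected by directed acyclic graph* (SAP, statistical considerations for Aims 1 and 2). This text directly follows the initiation, continuation and persistence models. Its main exposures are age, pregnancy status, relationship status and substance use. PrEP use is not among them, and a set chosen for the effect of age on persistence is not the set needed for the effect of PrEP on HIV or birth outcomes.
- *Inverse probability weights* (same section). These address loss along the cascade, not selection into PrEP.
- *Further analyses to be considered* (protocol section 6; SAP statistical considerations and 2.5). Optional, HIV only, no method named.

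Nothing is committed for any of the four outcome groups.

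**3. Size of bias, illustration only.** For one binary risk factor that multiplies the outcome rate by R, with prevalence p1 in users and p0 in non-users and no PrEP effect, the apparent ratio is

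[1 + p1(R − 1)] / [1 + p0(R − 1)].

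Assumed: 30% of women carry the factor, and overall uptake is 60%.
- R = 3, uptake 80% in carriers and 51% in others: p1 = 0.3 × 0.8 / 0.6 = 0.40 and p0 = 0.3 × 0.2 / 0.4 = 0.15. Ratio = 1.80 / 1.30 = **1.38**.
- R = 2, uptake 70% and 56%: p1 = 0.35 and p0 = 0.225. Ratio = 1.35 / 1.225 = **1.10**.

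Over a wider assumed grid (R from 1.5 to 3, prevalence 20–50% in users and 20–40% in non-users) the factor runs from 0.78 to 1.43. The ratio of 0.57 for women cited in the protocol background would then appear as 0.57 × 0.78 = 0.44 up to 0.57 × 1.43 = 0.81.

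**4. Bias against precision.** Assume a true HIV rate ratio of 0.57.

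| Incidence off PrEP | Events off / on | SE of log ratio | 95% limits multiply or divide by |
|---|---|---|---|
| 10.7 per 100 PY (protocol background, an upper figure) | 77 / 66 | 0.168 | 1.39 |
| 2 per 100 PY (assumed) | 14 / 12 | 0.388 | 2.14 |

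At the high incidence a factor of 1.38 is about as large as the random error. At the low incidence, random error dominates for HIV.

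Birth outcomes rest on up to about 1200 births. Assume 10% adverse outcomes in non-users and no PrEP effect. An unadjusted two-sided 5% test of 720 against 480 would reject 8.3%, 18.5% and 34.8% of the time for bias factors of 1.1, 1.2 and 1.3. The SAP attaches no test to these outcomes; the figures show what an unadjusted reading would do.

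**5. Limits of adjustment.** Follow-up creatinine is scheduled for women on PrEP only (protocol section 5, laboratory tests, and protocol Table 1), so creatinine change has no planned non-user follow-up data. The side-effect questions in follow-up Step 5 are also put to women on PrEP. Adjustment cannot create the missing comparison group.

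**The case against.** The strongest reply is that these are secondary and descriptive outcomes. The verbs are describe and summarise, no hypothesis or power is attached, and unadjusted frequencies by exposure answer that aim. This is largely fair, and it is why the unadjusted figures should stay. It does not remove the need for a caution, given the comparison wording in Table 1 and the references to intervention and treatment effects.

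Second, the graph-based covariate text says it applies to each outcome, and Aim 1 includes HIV and adverse events. The text is ambiguous, and the documents never call these rates crude; that follows from the absence of a commitment. The placement and the named exposures favour the narrower reading.

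Three stronger readings are tempting and not supported:
- *That counts and crude rates are all the plan allows for HIV.* Both documents leave further HIV analyses open.
- *That these contrasts feed the Aim 3 model.* The protocol says cohort results will parameterise the model, in terms of initiation, retention and adherence. It does not say that the user/non-user HIV ratio supplies efficacy, and it does not mention the adverse-event, birth or growth comparisons there.
- *That 1.10 to 1.38 estimates the bias in this study.* It rests on assumed inputs and fixed ever/never groups, whereas the planned exposure is recent or on/off use.

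**Conclusion.** The point holds. PrEP use is self-selected, the SAP plans user/non-user comparisons of HIV, maternal, birth and infant-growth outcomes, and it commits to no adjustment for any of them. Following the plan as written gives confounded contrasts.

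The direction and size of the bias cannot be derived from the documents; the ratios of 1.10 to 1.38 show only that moderate, plausible selection is enough to matter. Confounding is likely to matter most for birth and growth outcomes, where numbers are large. For HIV it depends on incidence: if events are few, imprecision will be the larger problem. This is a correctable gap in a secondary analysis and does not affect the cascade proportions that are the primary outcomes.

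**What to change.** In SAP Table 1 and sections 2.5 and 2.6:

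- Keep the unadjusted figures and label them descriptive and not causal.
- Beside them, report an adjusted ratio or difference. Use Poisson regression with robust standard errors and time-updated PrEP use for HIV and for adverse events ascertained in all women, and regression for birth and growth outcomes. State one definition of PrEP use for each analysis, since section 2.6 and the adverse-event shell now differ.
- Adjust for covariates already collected: age, partner's HIV status, STI, relationship status, number of partners, substance use, gestational age and site. If HIV events are few, use a single propensity score in place of separate covariates.
- Do not present creatinine change as a user/non-user comparison, and limit side-effect contrasts to items asked of all women.
- State that time-varying and unmeasured confounding remain. Baseline covariates with time-updated exposure do not remove them.

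The cost is SAP wording, added columns in the shells and extra analysis, with no new data collection. The adjusted estimates may be imprecise, especially for HIV.

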## 2. Analysis Plan

### 2.1 Preliminary evaluation of data:

#### ***Purpose:***

To identify issues that will affect our approach to the primary analysis. Specifically:

- (1) To summarize the amount of missing data for key variables,
- (2) To summarize time between baseline and follow-up key measurements, and
- (3) To examine the distributional characteristics of key variables in order to detect potential data entry/reduction errors.

#### ***Methods:***

Relevant approaches may include:

- (1) Inclusion of all participants in data evaluation regardless of intervention group,
- (2) Tabulation of descriptive statistics for key variables (including missing observations),
  - a. Key variables include: age, education, relationship status, partner's HIV status, IPV, depression, substance use, PrEP knowledge, STI status, persistence to PrEP at v2 and beyond, SAEs, birth outcomes
- (3) Histograms, quantile plots of baseline levels and follow-up measures and changes in those measures.

### 2.2. Description of study process

#### ***Purpose:***

To compare how the study unfolded with the pre-trial plan in order to determine if changes in the pre-trial analysis plans are warranted.

#### ***Methods/Approach:***

- (1) Study flow figure (see Continuation Flowcharts)
- (2) Number screened per week and month (target= 18 per week, 72 per month) vs number enrolled
  - a. The projected sample size for the study is 1200 women enrolled until 12-months postpartum (estimated mean of 18-months follow-up).
- (3) Subjects initiating PrEP compared to those who do not
  - a. Estimated that 60% of women (n=720) will initiate PrEP during the study period (versus approximately 40% who will not).
- (4) Continuation and persistence by group
  - a. Assumed that approximately 75% of women on PrEP (n=540) will continue on PrEP at 12-months (defined as not missing >1 study visit among women on PrEP);
  - b. Assumed that 70% of those retained in care (n=378) will adhere to PrEP during at-risk periods.
- (5) Final completion rates
  - a. Compare final number of participants who enroll in study, who initiate PrEP, who are retained in care, and who adhere to PrEP to sample sizes needed to yield 80% power (i.e., n=1200, 720, 540, 378, respectively).
- (6) Number of subjects in analysis data sets
  - a. Consider number of participants that will potentially be excluded from analyses because of withdrawal from study, missing data on key covariates or outcomes, etc.

